7.3 LOST TO FOLLOW-UP

A participant will be considered lost to follow-up if study staff are unable to contact the participant after at least 15 attempts for the 6-month, 12-month, or 24-month follow-up survey.

The following actions must be taken if a participant is unreachable by study staff:

[figure not shown]
- Study staff will seek to contact family of an unreachable patient, or the patient of an unreachable family.
- Study staff will query the electronic health record or ask primary care clinic staff if the patient has moved or had a change in health status.
- If these efforts are not successful, the participant will be noted as having been lost to follow up.

If a patient/family dyad are lost to follow-up, we will use all available data that are observed on that dyad in analyses. For patients who are lost to death, we will attempt bereavement surveys with family caregivers two to three months after death, following best practices.

8 STUDY ASSESSMENTS AND PROCEDURES

8.1 ENDPOINT AND OTHER NON-SAFETY ASSESSMENTS

A description of the screening and enrollment procedures is provided in section 5.5 of this protocol. Participants will be assessed at baseline (after consent and before randomization) (**B6, C3**), and 6 (**B7, C4**), 12 (**B8, C5**), and 24 months (**B9, C6**) post-randomization. Bereavement surveys will be administered via telephone or web survey to enrolled family caregivers two to three months after the death of the patient in lieu of subsequent assessments (**C7**). For the 6, 12, and 24- month surveys, the window for data collection will be +/- 30. We will attempt bereavement surveys with family caregivers two to three months after death, following best practices. A summary of information to be collected from participants at each assessment are further elaborated on in the text that follows and discussed in detail in section 9.0 of this protocol.

* = See Study Participant Flow Detailing Recruitment Process clarifying approach to recruiting patients with impaired capacity whose LAR is not the caregiver

Enrollment

Enrollment officially occurs at the time of providing informed oral consent (see exhibit, above), or at such a time that it is confirmed by study staff that both patient and caregiver have been administered the oral consent script with a research staff member and orally consented to participate. Enrollment occurs prior

to patient and caregiver participants' completion of the baseline assessment and randomization. The date of study enrollment will be tracked and documented for each participant.

Baseline Assessments

Study staff will administer baseline patient surveys (**B6**). Caregivers will be given the option to self-administer the baseline survey on hard (paper) copy or using a REDCap survey link. The following information, further detailed in the Schedule of Evaluations (see 6.1 of our Manual of Procedures) will be collected during surveys at baseline:

- Patient characteristics (demographic factors, health status, interpersonal relationships with caregiver and family, quality of life)
- Family caregiver characteristics (demographic factors, health status, interpersonal relationship with patient and family, caregiving intensity and appraisal)
- Primary care interactions and communication (therapeutic alliance, shared decision-making, frequency and mode of contacts, use of patient portal)
- Patient and family experiences (quality of communication, engagement in advance care planning)
- Alert events, adverse events

After providing informed consent (**A1**), primary care clinicians will be asked to provide their demographic information and information about characteristics of their practice in a brief questionnaire (**A2**). Clinicians will be asked to allow research staff to identify potentially eligible established patients who are scheduled for an upcoming visit from the clinic's electronic scheduling system.

ACP facilitators/ interventionists will complete a baseline assessment prior to training (**E2, E3**) and a post-training survey (**E4**) upon completion of the training.

Follow-up Assessments

The window during which surveys are conducted will be +/- 90 days for each regularly scheduled follow-up assessment as noted in the Schedule of Evaluations. The following information, further detailed in the Schedule of Evaluations (see 6.1) will be collected at 6 (**B7, C4**), 12 (**B8, C5**), and 24 months (**B9, C6**) follow-up:

- Patient characteristics (health status, living arrangement, mutuality with family caregiver, quality of life)
- Family caregiver characteristics (health status, living arrangement, mutuality with older adult, caregiving intensity and appraisal)
- Primary care interactions and communication (therapeutic alliance, shared decision-making, frequency and mode of contacts, use of patient portal)
- Patient and family experiences (quality of communication, engagement in advance care planning)
- Alert events, adverse events

Should participants be screened positive for symptoms of depression or anxiety, they will be notified of this finding (**G1**). They will be asked if they would like an educational brochure about depression (**G4, G5**) or anxiety (**G3, G5**) (as appropriate), or if they would like the interventionist to notify their primary care clinician of this finding (**G2**).

Primary care clinicians will be asked to provide follow-up information about characteristics of their practice in a brief survey after all patients have been enrolled (**A4**).

Follow up assessments for ACP facilitators/ interventionists are detailed in section 6 of this protocol.

Completion/Final Evaluation

If a clinician drops out before randomization occurs, he/she will be replaced. If a clinician drops out after randomization, but patient/family dyads are evaluable, we will perform an intent-to-treat analysis for that dyad. If a patient/family dyad are lost to follow-up, we will use all available data that are observed on that dyad in analyses. For patients who are lost to death, we will attempt bereavement surveys (**C7**) with family caregivers two to three months after death, following best practices. Patients and/ or caregivers that are assigned to the intervention who have completed the study, including those who are lost to death, will be invited to share their experience with the intervention through a final qualitative telephone/ video interview. The following information, further detailed in the Schedule of Evaluations (see 6.1) will be collected:

- Quality of end-of-life care, receipt of burdensome care at the end of life
- Surrogate decision-making experience (decisional conflict, decisional regret)
- Family caregiver symptoms of anxiety and depression
- Adverse events

8.2 SAFETY ASSESSMENTS

Participant safety will be monitored following the protocol outlined in our Data and Safety Monitoring Plan and Manual of Procedures. We follow the Office of Human Research Protections' guidance in our approach to defining and identifying Serious Adverse Events, Adverse Events, and Unanticipated Problems. A description of safety assessments and reporting is further described in the following text.

8.3 ADVERSE EVENTS AND SERIOUS ADVERSE EVENTS

8.3.1 DEFINITION OF ADVERSE EVENTS

We follow the Office of Human Research Protections' guidance in our approach to defining and identifying Serious Adverse Events, Adverse Events, and Unanticipated Problems. **Adverse events** are any untoward or unfavorable medical occurrence, including any abnormal sign, symptom, or disease identified by any member of the research team that may occur at any time following consent of participants whether or not it is considered related to participation in the research. Advance care planning is already routinely offered in primary care and uptake of intervention processes will be at the discretion of patients and families. Based on our previous work and studies in this area by others, there is a small risk that participants will become anxious/agitated due to the prospect or experience of advance care planning. Adverse events that result from study participation are expected to be mild and psychological in nature. Interventionists will be trained to monitor, record, and manage such events and make effective referral.

8.3.2 DEFINITION OF SERIOUS ADVERSE EVENTS

Serious adverse events are any adverse event temporally associated with research participation that: 1) results in death; 2) is life-threatening; 3) requires inpatient hospitalization or prolongation of existing hospitalization; 4) results in a persistent or significant disability/incapacity; 5) results in a congenital anomaly/birth defect; or 6) any other adverse event that, based upon appropriate medical judgment, may jeopardize the subject's health and may require medical or surgical intervention to prevent one of the other outcomes listed in this definition. This is a minimal risk behavioral intervention and we do not anticipate any serious adverse events. The trial will be conducted in a population of older adults 80 years

and older with cognitive impairment and the significance of our study rests in part on low completion of advance care planning in the target population despite high rates of mortality and adverse health events (e.g., hospitalization, emergency department visits). We will monitor rates of serious adverse events by intervention group as a part of our analytic plan, but these events will not be systematically included in safety reporting as it is improbable that they will result from the intervention. If any deaths should occur, they will be reported by the principal investigator to the DSMB and National Institute on Aging Program Officer within 24 hours of initial notification.

8.3.3 CLASSIFICATION OF AN ADVERSE EVENT

8.3.3.1 SEVERITY OF EVENT

For adverse events (AEs) not included in the protocol defined grading system, the following guidelines will be used to describe severity.

- **Mild** – Events require minimal or no treatment and do not interfere with the participant’s daily activities.
- **Moderate** – Events result in a low level of inconvenience or concern. Moderate events may cause some interference with functioning.
- **Severe** – Events interrupt a participant’s usual daily activity and may require systemic drug therapy or other treatment. Severe events are usually potentially life-threatening or incapacitating. Of note, the term “severe” does not necessarily equate to “serious”.

8.3.3.2 RELATIONSHIP TO STUDY INTERVENTION/EXPERIMENTAL MANIPULATION

Relatedness of adverse events, serious adverse events, and unanticipated problems will be evaluated on the basis of temporality and relation to intervention processes. Specifically, we will determine whether the event occurred subsequent to the patient/family having engaged in an advance care planning and having been triggered or caused by the prospect or experience of engaging in an advance care planning discussion and/or other processes and activities related to the intervention protocol.

8.3.3.3 EXPECTEDNESS

Unanticipated problems are unexpected, related or possibly related to participation in research, and suggest that participating in research poses greater risk of physical, psychological, economic, or social harm than previously known or recognized. Given the minimal risk of the study, the voluntary nature of patient/family participation, and the availability of advance care planning in mainstream primary care, unexpected problems are unlikely. Nevertheless, we will monitor the emergence of any unanticipated problems in the Aim 2 trial through interviews with patients, families, and trained interventionists.

8.3.4 TIME PERIOD AND FREQUENCY FOR EVENT ASSESSMENT AND FOLLOW-UP

Should a significant adverse event occur that is unanticipated and related to the intervention, it will be reported to NIA Program Officer and to the DSMB Chair or to the designated DSMB member within 48 hours of the study’s knowledge of the significant adverse event. All other significant adverse events will be reported to the NIA Program Officer and to the DSMB (or a Safety Officer) quarterly. Given that some advance care planning visits may occur in people’s homes, there is the potential that facilitators will encounter a potential emergency situation that is not related to study participation (e.g., dehydration, environmental risk, medical emergency). We refer to such events as **safety alerts** and have well developed procedures for monitoring and management (see adverse event reporting procedures below). All safety alerts will be reported to the NIA Program Office and DSMB semiannually.

8.3.5 ADVERSE EVENT REPORTING

Adverse events will be reported per IRB policies. All members of the DSMB will receive copies of all safety reports at the time of submission to the IRB of the Johns Hopkins Bloomberg School of Public Health. In addition, a listing of all adverse events and their attribution (e.g., study related, intervention related, or unrelated to study or treatment) will be provided to the DSMB biannually.

8.3.6 SERIOUS ADVERSE EVENT REPORTING

Should a significant adverse event occur that is unanticipated and related to the intervention, it will be reported to NIA Program Officer and to the DSMB Chair or to the designated DSMB member within 48 hours of the study's knowledge of the significant adverse event. All other significant adverse events will be reported to the NIA Program Officer and to the DSMB (or a Safety Officer) quarterly.

8.3.7 REPORTING EVENTS TO PARTICIPANTS

N/A

8.3.8 EVENTS OF SPECIAL INTEREST

N/A

8.3.9 REPORTING OF PREGNANCY

N/A

8.4 UNANTICIPATED PROBLEMS

8.4.1 DEFINITION OF UNANTICIPATED PROBLEMS

Unanticipated problems are unexpected, related or possibly related to participation in research, and suggest that participating in research poses greater risk of physical, psychological, economic, or social harm than previously known or recognized

8.4.2 UNANTICIPATED PROBLEMS REPORTING

Unanticipated problems are unexpected, related or possibly related to participation in research, and suggest that participating in research poses greater risk of physical, psychological, economic, or social harm than previously known or recognized. Given the minimal risk of the study, the voluntary nature of patient/family participation, and the availability of advance care planning in mainstream primary care, unexpected problems are unlikely. Nevertheless, we will monitor the emergence of any unanticipated problems in the Aim 2 trial through interviews with patients, families, and trained interventionists. Unanticipated problems that emerge will be reported by the principal investigators to the DSMB and National Institute on Aging Program Officer within 48 hours of initial notification to the project team.

8.4.3 REPORTING UNANTICIPATED PROBLEMS TO PARTICIPANTS

N/A

9 STATISTICAL CONSIDERATIONS

9.1 STATISTICAL HYPOTHESES

Objectives and hypotheses related to primary outcomes are as follows:

We test the efficacy of SHARE on quality of communication (primary outcome) and advance care planning processes (secondary outcomes) at 6 months among primary care patients with cognitive impairment (mild-severe) and family caregiver dyads. We hypothesize that as compared with the control group, caregivers in the intervention group will report better quality of communication about end of life care with primary care clinicians at 6 months (primary outcome).

Objectives and hypotheses related to secondary outcomes are as follows:

We further test the efficacy of SHARE on advance care planning processes at 6 months. We hypothesize that intervention caregivers will be more highly engaged in advance care planning than control caregivers as measured by caregiver-reported readiness to engage in advance care planning and having documented advance directive in the patient's electronic health record at 6 months. We expect patient-reported outcomes will mirror those reported by caregivers and that outcomes will be achieved without adversely affecting the therapeutic alliance with the primary care clinician or perceptions of shared decision-making with the primary care team.

For patients who die by 24 months, we examine quality of end of life care and bereaved family caregiver experiences with medical decision-making. We hypothesize caregivers in the intervention group will report higher quality of end-of-life care than those in the control group as measured by the Satisfaction with Care at the End-of-Life in Dementia scale. We expect that bereavement outcomes will be superior among intervention caregivers than control group caregivers as measured by less decisional conflict, less decisional regret, and fewer symptoms of anxiety and depression. Finally, we expect that decedents in the intervention group will be less likely to experience burdensome care at the end of life than decedents in the control group.

We expect patient-reported outcomes will mirror those reported by caregivers and that outcomes will be achieved without adversely affecting the therapeutic alliance with the primary care clinician.

9.2 SAMPLE SIZE DETERMINATION

Sample size is based on our ability to detect a clinically meaningful effect for our primary outcome at 6 months, following intention to treat. Because we randomize at the individual level, clinic-level cluster effects are not included in power calculations. From prior trials we assume an unadjusted intervention effect of 0.30 standard deviation units (SDUs).^{51,84} Incorporating baseline QOC scores as a covariate and assuming correlation of 0.65 between baseline and 6-month QOC scores yields a covariate-adjusted effect size of 0.39 SDUs. Based on an enrolled sample of about 248 dyads and attrition of 10%, a retained sample of 222 will provide more than 80% power to detect a covariate-adjusted effect of 0.39 using a two-sided test and a type 1 error rate of 0.05. For secondary outcomes, studies in similar samples^{25,57-59} suggest 50% mortality by 24 months. With 124 observations, power exceeds 80% to detect decreases of 20% or more in burdensome care (e.g. 30% vs. 10%). Assuming 25% attrition, 92 surrogate responses will be sufficient to monitor the effects of SHARE on satisfaction with end-of-life care, surrogate decision-making, and bereaved family outcomes; measures that are essential to assessment of quality of end-of-life care, as well as provide effect sizes to guide future trials of advance care planning in primary care populations.

9.3 POPULATIONS FOR ANALYSES

The populations for analyses encompass a sample of about 248 person-family dyads who meet eligibility criteria specified in Section 5 of this protocol. The table below summarizes information that will be assessed from patient and family participants.

| 9.3 Table of Assessments | | | | | | | | | | | | |
|---|---|---------------------------------|-------|--------------------------------|------------|-------------|----|----|-----|-----|-----|--|
| Construct | Measure | Items | Range | Validity | Source | Outcome | BL | 6M | 12M | 24M | EOL | |
| Outcomes @ 6 Months, Patient and Family Experience | | | | | | | | | | | | |
| QOC (Primary) | Quality of EOL Communication ^{51,84-87} ; General QOC Subscale and Global (Secondary) | 7 7 | 0-70 | $\alpha=0.79$ $\alpha=0.91$ | P, F | F@6M | X | X | X | X | | |
| ACP (Secondary) | Sudore 4-item ACP engagement μ ^{88,89} | 4 | 0-20 | $\alpha=0.84$ | P, F | F@6M | X | X | X | X | | |
| | Advance Directive Completion ²⁰ | -- | Y/N | -- | EMR | E@6m | | X | X | X | X | |
| Outcomes @ EOL, Quality of Care and Surrogate Decision-Making Experience | | | | | | | | | | | | |
| Quality of EOL (Primary) | Satisfaction w/ Care at the EOL in Dementia ^{51,90} | 10 | 10-40 | $\alpha=0.90$ | F | F@EOL | | | | | X | |
| Surrogate Decision- Making (Secondary) | Decisional conflict scale ⁹¹⁻⁹³ | 16 | 0-100 | $\alpha=0.78$ | F | F@EOL | | | | | X | |
| | Decisional regret – Brehaut ⁹⁴⁻⁹⁶ | 5 | 0-100 | $\alpha=0.81-0.92$ | F | F@EOL | | | | | X | |
| | Anxiety: GAD-7 ^{97,98} | 7 | 0-21 | $\alpha=>0.92$ | F | F@EOL | X | X | X | X | X | |
| EOL care (Secondary) | Burdensome care | | | | EMR/F | EMR@ EOL | | | | | X | |
| Primary Care Interactions and Communication | | | | | | | | | | | | |
| Therapeutic alliance | Human Connection Scale ⁹⁹⁻¹⁰³ | 16 | 16-64 | $\alpha=0.90$ original | F | - | X | X | X | X | | |
| Shared Decision- Making | CollaboRATE μ ¹⁰⁴⁻¹⁰⁷ | 3 | 0-100 | $\alpha=0.89$; 0-9/item | P, F | - | X | X | X | X | | |
| Primary Care Interactions | Frequency/Mode of Contacts ^{29,108,109} (IH) | 5 | -- | Homegrown | F, E | - | X | X | X | X | X | |
| | Use of patient portal | -- | -- | -- | EMR | - | X | X | X | X | X | |
| Implementation, Fidelity/Implementation Processes, Clinic Context (Note: these items will be limited to intervention participants) | | | | | | | | | | | | |
| Acceptability | Acceptability: Recruitment & retention | Consort diagram | | | | - | | | | X | | |
| Fidelity | Having had 1+ ACP discussion (ACP) | 5 | Y/N | | P, F, I | - | | X | X | X | | |
| | Fidelity to Respecting Choices ^{82,110} | | | | P, F, I, A | - | | X | X | X | | |
| | Registration for Patient Portal | | | | F, E | - | X | X | X | X | | |
| Sustainability | Clinic continues intervention ¹¹¹ | Clinic/Health system leadership | | | | | X | | | | | |
| Patient and Family Characteristics, Caregiving Circumstances | | | | | | | | | | | | |

| | | | | | | | | | | | |
|-----------------------------|---|----|--------|-----------------------------|--------|---|---|---|---|---|--|
| Demographic Factors | Age, Gender, Education, Race/Ethnicity, CG Work ¹¹² , P/CG type of relationship, Health literacy screen ¹¹³ | 14 | | | P/F, F | - | X | | | | |
| | Living arrangement | 1 | | | P/F, F | - | X | X | X | X | |
| Interpersonal relationships | Caregiver/receiver Mutuality (Love, shared activities & values, reciprocity) ^{30,114} | 15 | 0-4 | $\alpha=0.93$ | P, F | - | X | | | | |
| | Family Apgar (family function) ^{115,116} | 5 | 0-20 | $\alpha=0.94$ | P, F | - | X | | | | |
| Health | Modified Telephone Interview for Cognitive Status | 12 | 0-50 | | P | - | X | | | | |
| | Self-rated health, PHQ-2, GAD2 (P) ^{117,118} | 3 | Likert | | P/F, F | - | X | X | X | X | |
| Quality of Life | Quality of Life-AD ¹¹⁹⁻¹²¹ | 13 | 13-52 | $\alpha=0.84$; ICC>0.75 | P/F | - | X | X | X | X | |
| | EuroQOL-5D, ^{122,123} | 6 | | | F | - | X | X | X | X | |
| Caregiving Circumstances | Intensity: Frequency, Type of Help ¹²⁴ | 8 | | Homegrown | F | - | X | X | X | X | |
| | Caregiver self-efficacy ^{125,126} | 4 | 5-20 | Not reported ¹²⁶ | F | - | X | X | X | X | |
| | 12-Item Zarit Burden Int + 1 global ¹²⁷⁻¹²⁹ | 13 | 0-60 | 0.87 | F | - | X | X | X | X | |

Source: P=patient; F=family caregiver; E=EMR; I=interventionist facilitator; A=audiotapes; C=clinic Note: μ =Modified to reflect family perspective.

9.4 STATISTICAL ANALYSES

9.4.1 GENERAL APPROACH

Quantitative Strand. The objective of this study is to test the efficacy of SHARE on quality of communication (QOC) at 6 months. Analyses will be performed using SAS statistical software, with each dyad as the unit of analysis. We will use intention-to-treat analyses as the primary method of analysis; data from all participants will be analyzed as members of their assigned study group. **Primary outcome:** We will test the effects of SHARE on improved QOC compared to usual care at 6 months. We will use hierarchical analyses of covariance on the 6-month (**B7, C4**) QOC score with treatment group as the primary independent variable and baseline QOC score as the primary covariate. Other baseline characteristics (individual- or practice-level variables) will be covariates if there is imbalance on these measures by treatment group or if they are significantly correlated with 6-month QOC after adjusting for baseline QOC score. A multilevel design will be implemented using SAS Proc MIXED with dyads (level 1) nested within clinics (level 2) that will allow us to enter and control for clinic-level covariates (size and characteristics of patient panel, staff, location). **Secondary outcomes and supplemental analyses:** In addition to the primary outcome, numerous comparisons will be conducted for secondary outcomes, measures of implementation, and supplemental analyses for clinically relevant subgroups and maintenance of effects at 12 and 24 months. We will examine the maintenance of intervention effects at 12 (**B8, C6**) and 24-months (**B9, C7**) by extending the multilevel model to include a longitudinal or within-person level, and trajectories of treatment impact over time will be estimated with linear longitudinal models.

For dichotomous outcomes (e.g., newly documented advance directive; burdensome care) we will construct multilevel logistic regression models using SAS Proc GLIMMIX. We will compute the effect size of primary and secondary outcomes to assess SHARE effects relative to other treatment effect estimates for advance care planning interventions reported in the published literature. The multilevel model will also be used to examine potential intervention moderation effects by examining two-way interaction effects between intervention (SHARE vs. control) and either dyad (e.g., cognitive impairment, caregiving relationship) or clinic characteristics (e.g., size, urban vs. suburban/rural) in separate models. Given the relatively modest sample size available for some secondary analyses, careful attention must be given to potential problems such as over-parameterization; thus only a limited number of covariates will be included in these models and potential interactions will be examined in separate models. We will examine rates of recruitment and retention, the timeliness and completeness of collected data,¹³⁰ and relative attrition rates (SHARE versus control protocol).⁶⁰

Qualitative Strand. At the end of the study, we will assess the acceptability of SHARE and the mechanism of observed effects.^{131,132} From audio-recordings of advance care planning facilitation sessions we will examine the duration, content, and receptivity to components of SHARE. After the completion of 24-month interviews or at any point after enrollment, we will seek invite select group of 12-20 dyads, all ACP facilitators and ACP fidelity raters to complete post-intervention in-depth interviews. These interviews will be audio-recorded, transcribed verbatim, and entered into NVivo 9 textual data analysis software. Qualitative analyses will be conducted by the study team concurrent to data collection using a framework approach^{132,133} involving familiarization with content, identification of a thematic analytic framework, data indexing, charting to abstract and distill key themes, and the mapping of charts to interpret themes and context-specific meaning. We will ensure rigor and minimize bias by comprehensively documenting data collection, regular study team debriefs, triangulation of diverse stakeholder perspectives and data

sources, attention to contradictory data elements, and reporting inter-rater agreement in data indexing.^{131,134} Findings from qualitative analyses will be cross-tabulated with quantitative analyses of efficacy for convergence to clarify the mechanism by which SHARE effects were observed and to identify how SHARE might be further refined and improved.

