Research staff responsible for the randomization protocol after enrollment will be aware of participant assignment status after it occurs. Allocation concealment will be ensured by blinding the PI and research staff conducting follow-up assessments and those responsible for coding study outcomes throughout the study. Only the study statistician, selected unblinded staff (and REDCap administrator), and members of the data and safety monitoring board (DSMB) will have access to unblinded data before study completion. As randomization occurs at the level of the person-family dyad, clinicians will care for patients in both groups. Clinicians will be blinded to group assignment. Patient-family dyads will have knowledge of group assignment, but no delineation will be made between group assignment indicating which is treatment or control. We will use group naming conventions of (Group A and Group B) to describe group assignment.

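### Beyond baseline QOC, covariates enter the primary 6-month model by observed imbalance or outcome significance, with no list, cut-off, timing or masking, so the primary analysis is not fixed in advance

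*Combined protocol and SAP*

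**What the plan says.** Section 9.4.1 of the combined protocol and SAP specifies an analysis of covariance of 6-month QOC on treatment group and baseline QOC, with dyads nested in clinics. It then adds two entry rules for further covariates. The first is imbalance: "Other baseline characteristics (individual- or practice-level variables) will be covariates if there is imbalance on these measures by treatment group". The second, an alternative to it, is association with the outcome: variables also enter "if they are significantly correlated with 6-month QOC after adjusting for baseline QOC score". It also says the multilevel model will "allow us to enter and control for clinic-level covariates (size and characteristics of patient panel, staff, location").

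Nothing elsewhere closes the choice:

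- Section 9.4.5 promises only a descriptive comparison of the groups at baseline and gives no criterion for imbalance.
- The caution in 9.4.1 about keeping covariates few concerns secondary analyses with modest samples, not the primary model.
- Sections 5.5.3 and 6.3 list who may see unblinded data before the study ends: "Only the study statistician, selected unblinded staff (and REDCap administrator") and the DSMB. No section says whether covariates are chosen on masked data, or when.

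Section 9.2 bases power on baseline QOC alone. It claims "more than 80% power to detect a covariate-adjusted effect of 0.39". The error rate behind that claim is given as "using a two-sided test and a type 1 error rate of 0.05".

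**The concern.** Two features of the rule are unsound, whatever cut-off is used. First, allocation is randomized 1:1 in blocks within clinician (section 5.5.3), so a baseline difference between arms is chance. A covariate earns its place by expected prognostic value, which can be named in advance. Second, the other trigger uses the 6-month outcome, so the model cannot be written down until outcome data exist.

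The missing cut-off makes this worse, because ordinary readings of imbalance differ widely in what they admit. What is at stake is whether the reported primary p-value comes from one model chosen beforehand or from one of several defensible models.

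The optional clinic-level covariates add to the openness and bring little. Treatment is balanced within clinician, and the number of clinics is small: up to 10 in the synopsis, up to 9 in section 4.1, and 124/31 = 4 if each clinic enrols the 31 intervention dyads given in section 5.5.3.

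**Working it through.** **1. The plan's own figure.** Inputs from section 9.2: "we assume an unadjusted intervention effect of 0.30 standard deviation units (SDUs"), "assuming correlation of 0.65 between baseline and 6-month QOC scores", 248 enrolled, 10% attrition, 222 retained (111 per arm).

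- Adjusted effect: 0.30/√(1 − 0.65²) = 0.30/√0.5775 = 0.395 (plan: 0.39).
- Power: Φ(0.39 × √(111/2) − 1.96) = Φ(2.905 − 1.96) = 0.828; by noncentral t, 0.825.
- For 80% power: 2 × (1.96 + 0.842)²/0.39² = 103.2, so 104 per arm. 208/0.9 gives 232 enrolled, below 248.

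The stated power reproduces, and it needs only baseline QOC.

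**2. How far readings of imbalance differ.** Assume 20 independent candidates. The standard error of a standardized mean difference (SMD) is √(2/111) = 0.134. Expected entries by chance:

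- p<0.05: 20 × 0.05 = 1.0.
- SMD>0.2: |z|>1.49, probability 0.136, so 20 × 0.136 = 2.7.
- SMD>0.1: |z|>0.745, probability 0.456, so 20 × 0.456 = 9.1.

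**3. Simulation of the rule.** 222 dyads, r = 0.65, 4,000 trials per scenario, clinics ignored. Assumed, not in the documents: 10 or 20 candidates, of which none or four are prognostic (coefficient 0.2 or 0.3 on the standardized residual outcome). The combined rule (imbalance or outcome significance) was applied at cut-offs 0.05, 0.10 and 0.20. The 11 readings are these three, each trigger alone at each cut-off, baseline QOC only, and all candidates.

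| Candidates (prognostic) | Type I error, one cut-off | Any of 3 cut-offs rejects | Any of 11 readings rejects | Power, baseline QOC only | Power, combined rule | Verdict differs across 3 cut-offs, planned effect |
|---|---|---|---|---|---|---|
| 10 (none) | 0.054-0.057 | 0.061 | 0.066 | 0.835 | 0.826-0.827 | 3.0% |
| 20 (none) | 0.049-0.050 | 0.059 | 0.070 | 0.816 | 0.791-0.803 | 4.7% |
| 10 (4 at 0.2) | 0.056-0.058 | 0.063 | 0.088 | 0.835 | 0.875-0.878 | 2.3% |
| 20 (4 at 0.2) | 0.050-0.052 | 0.060 | 0.092 | 0.834 | 0.865-0.868 | 4.5% |
| 20 (4 at 0.3) | 0.053-0.055 | 0.062 | 0.103 | 0.825 | 0.947-0.951 | 1.6% |

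The Monte Carlo standard error of a type I error near 5% is √(0.05 × 0.95/4000) = 0.0034. Across all 11 readings the verdict at the planned effect differs in 6.3-19.0% of trials.

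**4. More thresholds.** A second simulation used 12-30 assumed candidates, 1,500 trials per scenario and five imbalance thresholds (p<0.05, 0.10, 0.20; SMD>0.1, >0.2). One threshold applied mechanically gave type I error of about 4-6%, and the smallest p over the five gave about 6-7%. The verdict at the planned effect changed in about 3-8% of trials. With some candidates prognostic, power was 86-88% under the rule against 82-84% with baseline QOC only.

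**The case against.** The strongest defence is that the rule, used once at one threshold, works: type I error stays near nominal. The 6-10% figures take the most favourable of several models, which is a ceiling on what the open wording permits and not a forecast of conduct. The covariate behind the power calculation is already fixed. All of this stands and limits the size of the point.

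A reader might infer more than the documents support in four ways.

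- **That covariates are chosen with the treatment result in view.** The statistician has access to unblinded data, but no section says selection uses it. The outcome trigger can be run on pooled data without arm labels. The imbalance trigger needs labels but no outcomes. The defect is silence on masking and timing.
- **That the rule costs power.** It loses about 1-3 points when no candidate is prognostic and gains about 3-13 points when four are.
- **That every measure in Table 9.3 is a candidate.** Section 9.4.1 does not say so, and 9.4.5 mentions only demographic and health characteristics. The number of candidates is therefore an assumption.
- **That QOC carries the only confirmatory test.** The synopsis, Table 9.3 and section 9.4.2 also call satisfaction with end-of-life care primary.

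The clinic-level wording is permissive, and terms that add little to a within-clinician contrast also move the test little. That is a reason to drop them, not evidence of bias.

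**Conclusion.** The point holds in moderate form. The primary QOC model is not fixed in advance. One of its two entry rules rests on chance imbalance, the other on the outcome, and neither has a list, cut-off, timing or masking.

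A single mechanical threshold keeps type I error at about 5-6%. An open imbalance threshold can bring it to about 6-7%, and openness across all readings to about 10%. At the planned effect the threshold alone alters the verdict in roughly 2-8% of trials. These ranges rest on assumed numbers and strengths of candidates, and the tabulated simulation ignores clinic clustering. The finding that the model is left open does not depend on those assumptions. Gross inflation of type I error and a general power loss are not shown.

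**What to change.** In section 9.4.1, delete both data-driven triggers and the optional clinic-level covariates from the primary model. Before unblinding, name one closed model containing:

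- treatment group and baseline caregiver QOC;
- the randomization stratum: clinician, or clinic if clinicians have too few dyads, with that choice also settled beforehand;
- at most a few dyad variables measured before randomization and chosen on prior prognostic grounds, for example the caregiver's relationship to the patient.

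Cognitive severity qualifies only if it is measured before randomization on a defined common scale. Section 4.1 allows either TICS-m or AD-8, and a 6-month assessment for patients who could not communicate at baseline, so as it stands the variable would mix instruments and be post-randomization for some. The a priori subgroup factors in 9.4.7 are not automatically suitable either, since no section says they predict QOC.

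Report adjustment for chance-imbalanced or outcome-associated variables only as a labelled sensitivity analysis.

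The cost is a rewording of 9.4.1 plus a decision on the stratum term and the short list. Sample size does not change, since baseline QOC alone gives about 83% power. The small downside is that an unlisted variable that proves imbalanced or prognostic is handled only in the sensitivity analysis.
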